14.0 APPENDIX

I. RECIPIENT SCHEDULE OF EVENTS TABLE*

| TEST ¹ | At entry | During Therapy and Recovery ² | At Count Recovery after IND1 or IND2 | After Finishing All Therapies ⁶ | Relapse |
|---|----------|---|---|--|---------|
| Weight (Epic) | X | Daily | As clinically indicated | At 8 weeks and q3months x 2 years | |
| Height (Epic) | X | | | | |
| BSA (Epic) | X | At the beginning of treatment | As clinically indicated | | |
| PS (Epic) | X | | As clinically indicated | At 8 weeks and q3months x 2 years | |
| Comprehensive Geriatric Assessment (Research) | X | - | - | At 8 weeks | |
| ABC / DIFF (Epic) | X | ABC daily and ABC with diff daily when WBC reaches 500/uL until ANC >1500/uL for 3 days | As clinically indicated | Every 2 weeks or as clinically indicated | |
| Serum BUN/Cr/CA/MG/PO/AST/ALT/Bili/TP/ALB/K/NA/CL /CO3/Glu/CMV viral titre (Epic) | X | Weekly and as clinically indicated | As clinically indicated | At 8 weeks after last therapy and every 3 months for 2 years | |
| HLA antibody detection (serum preferred) | X | | X | At 8 weeks after last therapy | |
| Serum quantitative Beta-HCG testing for females (Epic) | X | - | - | - | |
| Bone marrow aspirate and biopsy with appropriate special studies (i.e. restaging/disease evaluation) (Epic) | X | Day 14 after induction ⁵ | at hematologic recovery after induction (4-6 weeks) | - | |
| Cardiopulmonary Testing ³ (Epic) | X | | | | |
| Immune Reconstitution Panel (Epic) | X | - | X | At 8 weeks after last therapy and every 3 months for 2 years | |
| Minimal Residual Disease (MDR)(Peripheral Blood) (Research) | X | | X | At 8 weeks after last therapy and every 3 months for 2 years | X |
| Minimal Residual Disease (MRD) (Bone Marrow aspirate ⁴ (Research) | X | | X (when BM bx is done to assess disease) | | X |

Chemo with Adoptive Haplo DLI

| | | | | | |
|---|-----------------|--|---|--|----------------|
| KIR typing (Research) | X | | | | |
| NK lysis assay (Research ⁸) | X | | X | At 8 weeks after last therapy | X |
| TEST¹ | At entry | During Therapy and Recovery² | At Count Recovery after IND1 or IND2⁶ | After Finishing All Therapies⁷ | Relapse |
| Microchimerism (Research) | X | | X | At 8 weeks after last therapy and every 3 months for 2 years | X |
| TCR sequencing (Research) | X | - | X | At 8 weeks after last therapy | X |
| Biomarkers of frailty (Research) | X | | X | At 8 weeks after last therapy | |
| PD1/PDL1/PDL2 expression (Research) | X | | X | At 8 weeks after last therapy | X |
| Cytokine Release Syndrome (Research) | | To be drawn before infusion and 2 days after infusion for IND1, IND2, and CON2 as applicable | | | |
| Toxicity monitoring (Grade 3-4) (Epic) | | Daily | Qo wk | Qo wk till 8 weeks after last therapy and then q 4 weeks for 12 more weeks | |
| Acute GVHD monitoring (Epic) | | Daily | Qo wk | Qo wk till 8 weeks after last therapy and then q 4 weeks for 12 more weeks | |

¹ Tests at entry are recommended to be done within 1 week before initiating therapy; however if there are no sig. change in patient's status and tests are less than 4 weeks old then they are acceptable; exceptions include bone marrow aspirate and biopsy and cardiopulmonary testing (acceptable if within 8 weeks)

² Therapy and recovery refer to the period while the patient is receiving induction (IND1 or IND2) or consolidation chemotherapy until count recovery and discharge

³ For cardiopulmonary testing, refer to section 5.1.

⁴If patient already had a bone marrow biopsy and this was not collected, ok to skip

⁵ Per investigator discretion

⁶ Count Recovery would be considered when the ANC count is >1000/uL

⁷ If any subjects do not complete all the therapies (i.e. Induction 1/2, Consolidation 1 and 2), they will be followed for survival, but do not need to complete any listed assessments

⁸Any leftover cells at q3months after completing therapy will be used to run NK Lysis, TCR sequencing, and PD1/PDL1/PDL2 expression research samples. Additional blood will not be drawn for this testing.

*Other labs may be performed/followed per institutional policy

II. DONOR SCHEDULE OF EVENTS TABLE

| Test | At Entry |
|---|----------|
| History, physical (Epic) | X |
| ABC / DIFF, Serum BUN/Cr/CA/MG/PO/AST/ALT/Bili/TP/ALB/K/NA /CL/CO3/Glu/CMV viral titre (Epic) | X |
| Serum quantitative Beta-HCG for females (Epic) | X |
| CXR (AP/lateral), EKG (12 lead) (Epic) | X |
| FACT labs* (Epic) | X |
| KIR typing (Research) | X |
| Microchimerism (Research) | |
| TCR sequencing (Research) | X |

*See appendix for standard FACT (Foundation for Accreditation of Cellular Therapy) labs. FACT labs must be drawn and final test results available within 7 days prior to infusion into the patient.

III. GVHD Grading Criteria

| GvHD | | | | | | |
|--------------------|----------------------------------|----------|--|--|-------------------------------|---|
| | Grade value for overall scoring: | +0 | +1 | +2 | +3 | +4 |
| | Skin | | Maculo-papular eruption over <25% of body area | Maculo-papular eruption over 25-50% of body area | Generalized erythroderma | Generalized erythroderma with bullous formation and often with desquamation |
| | Liver | | Bilirubin ≥ 2 -<3 mg/dl; SGOT 150-750 IU | Bilirubin ≥ 3 -<6 mg/dl | Bilirubin ≥ 6 -<15 mg/dl | Bilirubin ≥ 15 mg/dl |
| | Gut | | Diarrhea >500-1000 ml/day | Diarrhea >1000-1500 ml/day | Diarrhea >1500-2000 ml/day | Diarrhea >2000 ml/day; or severe abdominal pain with or without ileus |
| Overall GvHD Grade | | | | | | |
| Date Scored | Grade value for overall scoring | Skin | Liver | | Gut | ECOG Performance |
| I | +1 to +2 | 0 | | | 0 | 0 |
| II | +1 to +3 | +1 | And/or | +1 | 0 - 1 | |
| III | +2 to +3 | +2 to +3 | And/or | +2 to +3 | 2 - 3 | |
| IV | +2 to +4 | +2 to +4 | And/or | +2 to +4 | 3 - 4 | |

IV Toxicity Summary Form

| Toxicity | Grade | | | |
|----------|-------|--|---|---|
| | 3 | | 4 | |
| | | | | 5 |

Allergy/Immunology

| | | | | |
|--|---|---|-------------|-------|
| | Allergic reaction/hypersensitivity (including drug fever) | Symptomatic bronchospasm, requiring parenteral medication(s), with or without urticaria; allergy-related edema/angioedema | Anaphylaxis | Death |
|--|---|---|-------------|-------|

Cardiovascular (Arrhythmia)

| | | | | |
|--|--|---|--|-------|
| | Ventricular arrhythmia | Symptomatic and requiring treatment | Life-threatening (e.g., arrhythmia associated with CHF, hypotension, syncope, shock) | Death |
| | Cardiovascular/Arrhythmia – Other Specify: | Symptomatic and requiring treatment of underlying cause | Life-threatening (e.g., arrhythmia associated with CHF, hypotension, syncope, shock) | Death |

Cardiovascular (General)

| | | | | |
|--|-------------|--|-------|-------|
| | hypotension | Requiring therapy and sustained medical attention, but resolves without sequelae | Shock | Death |
|--|-------------|--|-------|-------|

Coagulation

| | | | | |
|--|---|---|--|-------|
| | Thrombotic microangiopathy (e.g., TTP or HUS) | Evidence of RBC destruction with creatinine ($>3 \times$ ULN) not requiring dialysis | Evidence of RBC destruction with renal failure requiring dialysis +/- encephalopathy | Death |
|--|---|---|--|-------|

Gastrointestinal

| | | | | |
|--|--------------------------------|--|--|-------|
| | Diarrhea (Autologous subjects) | Increase of ≥ 7 stools/day, or incontinence, or need for parenteral support for dehydration | Physiologic consequences requiring intensive care; or hemodynamic collapse | Death |
| | Stomatitis/mucositis | Painful erythema, edema, or ulcers preventing swallowing or requiring hydration or parenteral (or enteral) nutritional support | Severe ulceration requiring prophylactic intubation or resulting in documented aspiration pneumonia | Death |
| | Vomiting | ≥ 6 episodes in 24 hours over pretreatment; or need for IV fluids | Requiring parenteral nutrition; or physiologic consequences requiring intensive care; hemodynamic collapse | Death |

Hemorrhage

| | | | | |
|--|-----------|--|---|-------|
| | Hematuria | Persistent gross bleeding or clots; may require catheterization or instrumentation, or transfusion | Open surgery or necrosis or deep bladder ulceration | Death |
|--|-----------|--|---|-------|

Chemo with Adoptive Haplo DLI

| | | | | |
|--|----------------------|-----------------------|--|-------|
| | Other (specify site) | Requiring transfusion | Catastrophic bleeding, requiring major non-elective intervention | Death |
|--|----------------------|-----------------------|--|-------|

Infection/Febrile Neutropenia [Enter type/species/site at bottom of this block]

| | | | |
|---|---|--|-------|
| Infection (documented clinically or microbiologically) with grade 3 or 4 neutropenia (ANC < 1.0 x 10 ⁹ /L) | Present | Life-threatening sepsis (e.g., septic shock) | Death |
| Febrile neutropenia (fever of unknown origin without clinically or microbiologically documented infection) | Present | Life-threatening sepsis (e.g., septic shock) | Death |
| Infection without febrile neutropenia | Severe, systemic infection, requiring IV antibiotic or antifungal treatment, or hospitalization | Life-threatening sepsis (e.g., septic shock) | Death |

Infection Type: Species: Site:

| Event | Toxicity | Grade | | | |
|------------------|----------|-------|---|---|---|
| Date | | 2 | 3 | 4 | 5 |
| Neurology | | | | | |

| | | | | | |
|--|----------------------|--|--|---|-------|
| | Neuropathy - Cranial | | Present, interfering with ADL | Life-threatening, disabling | Death |
| | Neuropathy – Motor | | Objective weakness interfering with ADL | Paralysis | Death |
| | Neuropathy – Sensory | | Sensory loss or paresthesia interfering with ADL | Permanent sensory loss that interferes with function | Death |
| | Seizure(s) | Seizure(s) self-limited and consciousness is preserved | Seizure(s) in which consciousness is altered | Seizures of any type which are prolonged, repetitive, or difficult to control | Death |

Pulmonary

| | | | | | |
|--|---|--|--|---|-------|
| | Carbon monoxide diffusion capacity (DLco) | | ≥25% - < 50% of pretreatment or normal value | <25% of pretreatment or normal value | Death |
| | Dyspnea (shortness of breath) | | Dyspnea at normal level of activity | Dyspnea at rest or requiring ventilator support | Death |

Chemo with Adoptive Haplo DLI

| | | | | | |
|--|-----------------------------------|--|--|--|-------|
| | Hypoxia | | Decreased O ₂ saturation at rest, requiring supplemental oxygen | Decreased O ₂ saturation, requiring pressure support (CPAP) or assisted ventilation | Death |
| | Pneumonitis/pulmonary infiltrates | Radiographic changes and requiring steroids or diuretics | Radiographic changes and requiring oxygen | Radiographic changes and requiring assisted ventilation | Death |

Renal/Genitourinary

| | | | | | |
|--|---------------|--|------------------------------------|-------------------------------------|-------|
| | Creatinine | | >3 – 6 x ULN | >6 x ULN | Death |
| | Renal failure | | Requiring dialysis, but reversible | Requiring dialysis and irreversible | Death |

Secondary Malignancy

| | | | | | |
|--|--|--|--|---------|-------|
| | Secondary Malignancy - Other Specify type: (excludes metastatic tumors) | | | present | Death |
|--|--|--|--|---------|-------|

VOD

| | | | | | |
|--|--------------|--|---|--|-------|
| | Weight gain | | ≥10% or ascites | ≥10% or fluid retention resulting in pulmonary failure | Death |
| | Bilirubin | | >3 - 10 x ULN | >10 x ULN | Death |
| | Hepatic pain | | Severe pain; pain or analgesics severely interfering with ADL | disabling | Death |

V. Comprehensive Geriatric Assessment

The Comprehensive Geriatric Assessment is provided as a separate attachment.

VI. FACT Donor Test Requirements

Testing for the following infectious disease is performed within 30 days of donation for PBSC, Bone Marrow, and Directd Granulocyte donation, and within 7 days for DLI, NK Cell donation, on blood samples drawn on stem cell or other cellular therapy. Donors donating over a time period in excess of 30 days will have these tests repeated every 30 days (or 7 days if DLI or NK Cell). Unrelated cord blood donors are tested by the cord blood bank at the time of procurement of the cord blood donation. This information is provided to the transplant center through the NMDP data systems.

The testing panel for autologous and allogeneic adult donors not on IVIG supplementation (within 6 months) of the donation is listed below.

1. Hepatitis B Surface Antigen (HBsAg)^{1,2}
2. Hepatitis B Core Antibody (Anti-HBc)¹
3. Hepatitis C Virus Antibody (Anti-HCV)¹
4. HIV antibody (Anti-HIV 1/2/0)^{1,2}
5. HIV1/2 Nucleic Acid Testing (NAT)^{1,2}
6. Hepatitis C Virus NAT^{1,2}
7. Hepatitis B Virus NAT^{1,2}
8. HTLV I/II Antibodies Serum^{1,3}
9. CMV Immune Screen (Anti-CMV total antibodies)^{1,3}
10. CMV NAT-(if CMV positive Peds Only)²
11. Syphilis-Treponemapallidum antibody for initial screen
12. If Syphilis screen is reactive, a confirmatory test is performed using the RPR Card Test System
13. West Nile Virus NAT¹
14. Trypanosoma Cruzi (Chagas Disease)
15. ABO/Rh (Two separate sample collections i.e. NTL Panel and day 1 collection type and screen)
16. Red blood cell antibody screen

¹FDA Required testing

²FDA recommended. Obtain in all patients<6 months of age or on IVIG or unable to make endogenous antibody

³FDA required for products containing high WBC content (i.e. granulocytes, DLI, and mobilized peripheral blood)

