6.3 Treatment Plan

6.3.1 Induction therapy

Eligible subjects will receive induction chemotherapy with idarubicin (12 mg/m^2 intravenously for 3 days) and cytarabine (100 mg/m^2 intravenously for 7 days) starting Day 1 and ending Day 7 as described in Figure 1. Patients 80 years or older may receive 2 and 5 days of idarubicin and cytarabine respectively starting Day 1 and ending Day 5 (optional, at physician discretion). HLA-mismatched DLI will be administered Day 9

Chemo with Adoptive Haplo DLI

(DLI will occur on Day 7 for 5+2 regimen), approximately 24-48 hours following completion of chemotherapy at a dose of 1×10^8 CD3+ cells; however, due to logistics of planning infusions with staffing, donor availability, weekends/holidays, etc., it may be necessary to postpone cell infusion up to 96 hours, which will be allowed without being considered a protocol violation.

Subjects who experience no remission or partial remission will receive a second course of the identical induction chemotherapy (IND2). IND2 should include 7+3+DLI as per IND1, but if cells are not available as per 6.2.3, chemotherapy alone can be given without being considered a protocol violation.

Given the time constraints presented by the need to start induction chemotherapy as soon as possible, in some cases, it may not be logistically possible to administer cells with induction (e.g., obtaining insurance approval for clinical trial/DLI may take a while, and approval may not be back in time for a patient to receive cells). In these cases, patients would just receive standard induction chemotherapy and cells would be administered after CON1 in addition to CON2 (see below). Timing of correlative laboratory studies will be adjusted to match cell infusion. Guo et al. have reported improved outcomes with high cell doses (1×10^8 CD3+ cells/kg) administered after consolidation, even in patients who receive standard induction chemotherapy without cells.¹

¹Guo M, Hu KX, Liu GX, Yu CL, Qiao JH, Sun QY, Qiao JX, Dong Z, Sun WJ, Sun XD, Zuo HL, Man QH, Liu ZQ, Liu TQ, Zhao HX, Huang YJ, Wei L, Liu B, Wang J, Shen XL, Ai HS. HLA-mismatched stem-cell microtransplantation as postremission therapy for acute myeloid leukemia: long-term follow-up. *J Clin Oncol.* 2012 Nov 20;30(33):4084-90. doi: 10.1200/JCO.2012.42.0281. Epub 2012 Oct 8.

[figure not shown]

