6.4 Subject Evaluation

6.4.1 Clinical Evaluation

Subjects will be evaluated daily during induction and recovery from therapy while admitted to the hospital. Evaluation will include history and physical exam and toxicity monitoring, including acute GVHD monitoring. They will return for post-remission therapy and typically be re-admitted to our service for further treatment. In selected cases, subjects may remain outpatient with very close care and follow up per the treating team's discretion. Upon completion of therapy, they will be seen at least every other week until 8 weeks, after which they will be seen at least every 3 months for 2 years.

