For purposes of toxicity monitoring, each patient will be followed for unacceptable toxicity until a toxic event occurs or until 8 weeks after last cell infusion, whichever comes first. Accrual will not be suspended while collecting data for the interim analyses. However, as soon as a boundary within a stage in the table above is crossed, the study will be closed to further accrual. This design and the above boundaries will constitute our stopping rules for safety.

11.1.2 Efficacy: Evaluate the efficacy of HLA-haploidential DLI infusion combined with conventional induction and consolidation chemotherapy in terms of donor-recipient chimerism and microchimerism.

The assessment of efficacy will be conducted after collecting data for a maximum of 21 evaluable subjects. Our primary efficacy endpoint is the 1-year DFS rate following adoptive transfer. Using the chi-square test, we will test the null hypothesis is the CR rate will be ≤ 0.20 against the true hypothesis that 1-year DFS rate is >0.45 . With 21 patients, we can test this with approximately 84% power with one-sided alpha level of 0.05. Additional efficacy endpoints include the CR rate, overall response rate (CR + partial response), OS, and count recovery. CR and overall response rates will be calculated with one-sided 90% confidence interval. DFS and OS will be estimated using the method of Kaplan and Meier. All statistical analyses will be conducted in conjunction with our co-investigator, [name]., Assistant Professor of Biostatistics and Bioinformatics.

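### The footnote reducing non-completers to survival follow-up conflicts with the 8-week toxicity follow-up that feeds the safety stopping rule

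*Combined protocol and SAP*

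**What the plan says.** Section 11.1 (Safety) sets the follow-up for the primary safety endpoint: "each patient will be followed for unacceptable toxicity until a toxic event occurs or until 8 weeks after last cell infusion", whichever is first. It makes no exception for patients who stop early. The same section closes the study at 4 or more patients with unacceptable toxicity among 11, or 7 or more among 21.

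In Appendix I, the recipient schedule, the toxicity and acute GVHD rows have three entries:
- daily during therapy and recovery, which footnote 2 ends at count recovery and discharge;
- every other week in the column headed "At Count Recovery after IND1 or IND2", with no stated end;
- "Qo wk till 8 weeks after last therapy and then q 4 weeks for 12 more weeks" in the column headed "After Finishing All Therapies".

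In the second header row the last of these columns carries marker 7. (The first header row prints 6 there, but footnote 6 defines count recovery.) Footnote 7 concerns patients who do not complete both phases of treatment: "they will be followed for survival, but do not need to complete any listed assessments".

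Section 6.4.1 has a matching visit rule, "Upon completion of therapy, they will be seen at least every other week until 8 weeks", but does not say whether it reaches patients who stop early. Section 6.4.2(h) describes relapsed or refractory patients as leaving the study.

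On the timing of cells, section 6.3.1 states "HLA-mismatched DLI will be administered Day 9" for standard induction. If cells cannot be given at induction, "cells would be administered after CON1 in addition to CON2".

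**The concern.** Consolidation is given only to patients in CR (section 6.3.2), so the design itself produces patients who receive cells and never complete all therapies. Section 11.1 needs their toxicity outcome to 8 weeks after the last infusion. Footnote 7 releases them from the scheduled post-therapy checks that would supply it.

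The endpoint is not a simple yes or no. Under section 7.0, GVHD and DLI-attributable toxicity count only at a given grade and when lasting more than 7 days. Scheduled grading provides that directly; survival follow-up does not. The rule turns on single patients, and an event that goes unrecorded can only push the result towards tolerable.

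**Working it through.** **1. Who is exposed, and for how long**

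- *Cells at induction, no consolidation.* Infusion on Day 9 plus 56 days puts the end of the section 11.1 window at Day 65. Appendix I puts haematologic recovery at 4 to 6 weeks. If that is counted from Day 1 (an assumption), recovery falls on Days 28 to 42, leaving 65 − 42 = 23 to 65 − 28 = 37 days. Two things may fill them. Section 6.3.1 sends patients with no or partial remission to a second induction, which returns them to daily monitoring. The every-other-week entry after IND1 or IND2 is not waived, but has no stated end. Coverage may therefore be partial or complete; the text does not settle it.
- *First cells after CON1, stopping before CON2.* The every-other-week column is headed for IND1 or IND2, so it does not apply. After discharge, the only remaining toxicity and GVHD entries are in the column marked by footnote 7. The gap here comes from the column heading as well as from the footnote.
- *Patients in CR who go on to consolidation* are covered by the every-other-week entry or by daily monitoring.

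**2. Reproducing the plan's design**

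Inputs from section 11.1: n1 = 11, continue at 3 or fewer; n = 21, tolerable at 6 or fewer; null rate 0.40, alternative 0.20.

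P(tolerable) = Σ over x = 0 to 3 of P(X1 = x) × P(X2 ≤ 6 − x), with X1 ~ Bin(11, p) and X2 ~ Bin(10, p).

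At p = 0.40:

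| x | P(X1 = x) | P(X2 ≤ 6 − x) | product |
|---|---|---|---|
| 0 | 0.0036 | 0.9452 | 0.0034 |
| 1 | 0.0266 | 0.8338 | 0.0222 |
| 2 | 0.0887 | 0.6331 | 0.0561 |
| 3 | 0.1774 | 0.3823 | 0.0678 |

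The unrounded sum is 0.1496, against the stated 0.15. At p = 0.20 the same sum is 0.801, against 0.80. The stage 1 stopping probabilities are 0.704 and 0.161, against 0.7 and 0.16. The design reproduces.

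**3. Effect of exactly one missed event at p = 0.40**

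- *In a stage 2 patient.* Stage 1 is unchanged, but 7 true events are counted as 6. P(X1 ≤ 3 and X1 + X2 ≤ 7) = 0.0036 + 0.0251 + 0.0739 + 0.1123 = 0.215.
- *In a stage 1 patient.* Four true stage 1 events are counted as 3, and 7 in total as 6. P(X1 ≤ 4 and X1 + X2 ≤ 7) adds the x = 4 term, 0.2365 × 0.3823 = 0.0904, giving 0.305. (The x = 0 term includes a path with no stage 1 event to miss; it is worth less than 0.0002.)

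Both figures are conditional on one event being missed. They are not estimates of the trial's error rate.

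**The case against.** The strongest defence is that the texts can be reconciled: the marked column is for patients who finished, and section 11.1 is a specific toxicity rule that a general schedule footnote need not override. This does not remove the conflict. Footnote 7 is expressly about patients who did not finish, and it exempts no row. Sites working from the schedule would be entitled to stop the checks.

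Other parts of the defence stand and limit the point:
- Section 9.0 collects adverse events of grade 3 or more, all serious events to 30 days after the last DLI, and related ones after that. Section 6.4.2(d) provides for biopsy where GVHD is suspected. Severe GVHD lasting over a week is unlikely to pass wholly unnoticed.
- Re-induction and the unwaived every-other-week entry may cover much of the window after induction.
- For the CON1 route, deleting footnote 7 alone would not clearly close the gap.
- Section 12.1 anticipates no GVHD. That lowers the expected number of missed events, but the trial is meant to test this expectation.
- Evaluable is not defined in section 11.1. If non-completers were outside the 21, the footnote would not affect the boundary count, but the plan does not say so.

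A reader might infer that non-completers have no safety follow-up, or that the type I error is really 0.215 or 0.305. The documents support neither. Much is still captured, and neither the share of infused non-completers nor the share of their events that would be missed is given. Error rates built on assumed values for those shares would not be informative.

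**Conclusion.** The conflict is real and should be fixed, but its reach is limited. At risk is scheduled grading and timing of non-fatal acute GVHD and DLI-attributable grade IV toxicity, after discharge and within 8 weeks of the last infusion, in patients who received cells and did not complete treatment. The number of events lost cannot be derived and may be zero. The reason to act is that any loss favours a finding of tolerability and that one event matters: the conditional increases are 0.065 (0.215 − 0.150) and 0.155 (0.305 − 0.150). These assume a true rate of 0.40, independent patients, and that infused non-completers count in the 11 and the 21. The boundaries and sample size need no change.

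**What to change.** Reconcile footnote 7 with sections 6.4.1, 6.4.2(h), 9.0 and 11.1:

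1. State that the waiver does not apply to the toxicity and acute GVHD rows for any patient who received at least one cell infusion, including a first infusion after CON1. These rows continue until an unacceptable-toxicity event or 8 weeks after the last cell infusion, whichever is first. Anchor the window on the infusion, as section 11.1 does, and not on the last therapy.
2. State that the waiver covers the other listed assessments, such as research samples.
3. State that infused non-completers, including those described as going off study, count toward the 11 and the 21.

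The cost is an edited footnote, a sentence on who is evaluable, and a few already scheduled checks per infused non-completer. No new procedure is needed. One further burden is that attribution must be recorded for events arising after any later treatment within the window.

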7.0 EVALUATION CRITERIA AND DEFINITIONS

1. Standardized response criteria will be used following **National Comprehensive Cancer Network (NCCN)** recommendations found on the NCCN website: www.nccn.org.
2. GVHD will be graded with standard criteria (see Appendix II). Other toxicity will be graded as per the NCI Common Terminology Criteria for Adverse Events (CTCAE) version 4.0 (see Appendix III). Grade 3-4 will be reported.
3. Unacceptable toxicity will be defined as either:
 - a. Grade III or IV aGVHD of the gut or liver or Grade IV aGVHD of the skin lasting > 7 days;

Chemo with Adoptive Haplo DLI

- b. Other grade IV CTCAE toxicity attributable to the DLI (e.g. infusion reaction, and distinct from grade IV toxicity attributable to chemotherapy) and lasting > 7 days
 - c. Treatment-related mortality (TRM), keeping in mind that anticipated mortality from standard induction chemotherapy in the elderly ranges from 11% for subjects 55-65 years-old with ECOG 0 to 50% for subjects older than 75 years with ECOG 2 [1].
4. Disease-free survival (DFS) is the time from CR to relapse or death.
5. Overall survival (OS) is the time from start of therapy to either death or the last day of follow-up for that patient.
6. Event Free Survival (EFS) is the time from start of therapy to progression of AML or relapse or death.
7. Neutrophil recovery time is defined as the first of 3 consecutive days in which the ANC is $>0.5 \times 10^9/L$
8. Platelet recovery is defined as the first of 3 consecutive days in which the platelet count is $>20 \times 10^9/L$
9. PD1/PDL1/PDL2 expression (marker of T cell exhaustion)
- 10.

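### Subjects who stop in CR before the second consolidation have no required relapse follow-up and no stated DFS handling rule, so the primary 1-year DFS is at risk of bias

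*Combined protocol and SAP*

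**What the plan says.** - **Appendix I, footnote 7.** The rule opens "If any subjects do not complete all the therapies (i.e. Induction 1/2, Consolidation 1 and 2" and goes on: "they will be followed for survival, but do not need to complete any listed assessments". It does not separate subjects in CR from those who never reached it.
- **Section 7.0, item 4.** "Disease-free survival (DFS) is the time from CR to relapse or death". Item 6 defines EFS from the start of therapy, with progression, relapse or death as events.
- **Section 11.1.2.** "Our primary efficacy endpoint is the 1-year DFS rate following adoptive transfer". The test is a chi-square test and the DFS estimate is Kaplan-Meier. No censoring rule is given. Section 11.1 plans for 21 evaluable subjects but does not define evaluable.
- **Section 6.3.2.** Both consolidations are given to subjects who have already reached CR, so the DFS clock starts before either.
- **Section 6.4.1.** Clinic visits, later quarterly and lasting two years, are tied to finishing treatment: "Upon completion of therapy, they will be seen at least every other week until 8 weeks, after which they will be seen at least every" (the quarterly interval follows).
- **Section 6.4.2(h) and the Relapse column of Appendix I.** These list the samples to take from a patient who has relapsed. They set no schedule for finding relapse.

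**The concern.** A subject can reach CR, enter the DFS risk set, and then miss one or both consolidations because of toxicity, refusal or a change of treatment. From then on footnote 7 asks only for survival. The waived items include those that could show relapse after treatment: the blood count with differential and the peripheral-blood MRD test.

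Relapse is likely to be a frequent DFS event. Section 3.1 says that more than half of elderly responders to standard induction relapse within six months, which is inside the 1-year window. If these relapses are not collected, the primary result depends on how the subjects are classified, and the plan leaves that choice open until the data are seen. A relapse date that was never collected may not be recoverable later. EFS has the same gap.

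**Working it through.** **1. Does another section restore relapse follow-up?**

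| Place | What it provides | Does it cover a subject who stops in CR before the second consolidation? |
|---|---|---|
| 6.4.1 | Visits to 2 years | They start on completion of therapy. Even on a loose reading of completion, footnote 7 waives the listed assessments |
| 6.4.2(h), Relapse column | Samples at relapse | Only once relapse is known |
| Footnote 7 | Survival follow-up | Gives deaths, not relapses; no contact interval stated |

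None of these requires relapse to be sought or dated in such a subject.

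**2. The plan's own figure.** Section 11.1.2 says "With 21 patients, we can test this with approximately 84% power with one-sided alpha level of 0.05". The alternative is "the true hypothesis that 1-year DFS rate is >0.45". The null is worded as "the null hypothesis is the CR rate will be ≤ 0.20"; I read 0.20 as the null DFS rate, which is an assumption. Using the null variance for the critical value and the alternative variance for power:

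- null SE = √(0.20 × 0.80 / 21) = 0.0873
- alternative SE = √(0.45 × 0.55 / 21) = 0.1086
- power = Φ((0.25 − 1.645 × 0.0873) / 0.1086) = Φ(0.980) = 0.837

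This agrees with the stated 84%, so the sample size is not in question. The exact binomial version rejects at 8 or more of 21, with size 0.043 and power 0.803.

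**3. Weight of one subject.** With 21 in the denominator, one unrecorded relapse scored as disease-free adds 1/21 = 4.8 points. If the denominator is CR subjects only, the background CR rate of 30–65% in section 3.1 gives about 6 to 14 subjects (21 × 0.30 = 6.3; 21 × 0.65 = 13.7). Each such relapse then adds 1/14 to 1/6, about 7 to 17 points.

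**4. Upward case, illustration only.** Assume that overall true 1-year DFS is 0.20, and that k subjects relapse unrecorded, are alive at 1 year and are scored disease-free. There are two ways to hold the overall rate at 0.20:

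- (a) k is an average: P(Bin(21, 0.20 + k/21) ≥ 8)
- (b) k is fixed, and the other 21 − k subjects have rate 4.2/(21 − k): P(k + Bin(21 − k, 4.2/(21 − k)) ≥ 8)

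| k | (a) | (b) |
|---|---|---|
| 0 | 0.043 | 0.043 |
| 1 | 0.124 | 0.107 |
| 2 | 0.261 | 0.229 |
| 3 | 0.436 | 0.415 |

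**5. Downward case.** Assume that true DFS is 0.45, and that on average k subjects who are really disease-free at 1 year are counted as failures: P(Bin(21, 0.45 − k/21) ≥ 8). Power falls from 0.803 to 0.659 for k = 1 and 0.482 for k = 2.

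**6. What is missing.** The documents do not give the share of CR subjects who stop before the second consolidation, or the share of those who relapse, are alive at 1 year and go unrecorded. The realistic value of k cannot be derived.

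**The case against.** A reader might infer that relapse is not measured at all in these subjects. The documents do not go that far. Footnote 7 says that assessments are not needed; it does not say that relapse goes unrecorded. Section 6.4.2(h) expects some relapses to be identified in patients going off study, and ordinary care may find others. A subject who stops because of relapse already has a known event. The affected group is those who stop while still in CR.

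A reader might also infer that 1-year DFS is overstated and the primary test biased toward success. That needs a handling rule the plan does not give. Non-informative censoring would leave the Kaplan-Meier estimate unbiased, and counting these subjects as failures would understate DFS. The documents also do not show that everyone who stops has a poor prognosis: one possible reason is transplant, which section 3.2 describes as potentially curative.

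Two further points narrow the contrast with completers. Appendix I schedules no marrow for them after therapy, and their two-weekly blood count may instead be done as clinically indicated. The footnote marker is also unsteady: the post-therapy column carries 6 in one printed header and 7 in the other, so a reading confined to that column is possible. Yet that column holds the post-therapy tests that could reveal relapse, so the gap remains on that reading too.

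Finally, turning an assumed stopping rate into the same number of misclassified subjects would treat everyone who stops as relapsed, alive at 1 year and unseen. That is a ceiling, not an estimate.

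These objections limit the claim about direction and size. They do not supply the missing follow-up or the missing rule.

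**Conclusion.** The point holds as a gap in required data collection combined with an unstated analysis rule. Following the plan as written can lose relapse events from the primary endpoint in subjects who stop in CR before the second consolidation, and from EFS. The chi-square test needs each subject classified at 1 year, and the plan does not say how these subjects are classified.

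The primary 1-year DFS is therefore at risk of bias. Upward bias is plausible under two of the open choices, and downward bias under another. The size is unknown because the stopping rate is not given. What can be said is that a trial of 21 is sensitive: one misclassified subject moves the rate by 4.8 points and, in the upward case with overall true DFS held at 0.20, takes the exact false-positive rate from 0.043 to about 0.11–0.12. These figures rest on an all-21 denominator and on 0.20 being the null DFS rate. The change should be made, but the gap does not show that the design or its stated power is wrong.

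**What to change.** Amend footnote 7 so that, for every subject who reached CR, whether or not all therapies were completed, relapse status and date are recorded at least every 3 months until at least 1 year from CR, and to 2 years for the DFS and EFS estimates. The source can be routine clinical records or the treating physician. Research samples and scheduled study tests can stay optional for subjects who stop early.

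In section 11.1.2, state that these subjects stay in the DFS analysis, that relapse and death are the events, and that censoring is at the last date on which disease status was known. State also whether the tested 1-year rate uses all evaluable subjects or only those who reached CR, and how a subject censored before 1 year enters the chi-square test.

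The cost is a short chart review or call every 3 months for what should be a few subjects. Footnote 7 sets no interval for the survival contact, so the amendment would have to set one. No new procedure is needed, and the sample size and the stated power of about 84% do not change.
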